All participants in this study will be de-identified.

Outcomes

Hospitalisation outcomes of interest will include the following conditions.

Mother	ICD-10-CM
Still birth, preterm birth pregnancy complications	P95 Stillbirth ⁹ O60 Preterm labour Z37 Outcome of delivery 
 • Single stillbirth • Twins, one liveborn and one stillborn • Twins, both stillborn • Other multiple births, all stillborn O00-O99.9 Pregnancy, childbirth and the puerperium
Infant	
Certain conditions originating in the perinatal period	Newborn affected by maternal factors and by complications of pregnancy, labour, and delivery P00-P96
Early neonatal death, SIDS	Ill-defined and unknown causes of mortality R95-R99.9
Congenital anomalies (CVS, CNS, other)	Congenital malformations, deformations and chromosomal abnormalities Q00-Q99.9
Infectious Diseases (pertussis, , etc.)	Certain infectious and parasitic diseases A00-B99
Meningitis	Meningitis due to other and unspecified causes G03 
 •arachnoiditis NOS •leptomeningitis NOS •meningitis NOS •pachymeningitis NOS
Encephalitis	Encephalitis, myelitis and encephalomyelitis G04 
 •acute ascending myelitis •meningoencephalitis •meningomyelitis
Lower respiratory (bronchiolitis, asthma, pneumonia, acute unspecified LRTI, bronchiectasis, Acute bronchitis, lung abscesses/pyothorax	Diseases of the respiratory system J00-J99
Neurological	Diseases of the nervous system G00-G99

⁹ Information about stillbirths is recorded in the Mortality Collection. The Mortality Collection includes extra information about fetal and infant deaths, such as gestation and birth weight. The ICD codes we propose are: P95 Fetal death of unspecified cause Z37 Outcome of delivery, Z37.1Single stillbirth, Z37.3 Twins, one live born one stillborn, Z37.4 Twins, both stillborn, Z37.7 Other multiple births, all stillborn

Pregnancy duration will be classified using the gestational age field from the National Maternity Collection data set. This field gives the duration of pregnancy in number of completed weeks. Preterm will be defined as birth before 37 weeks gestation. Normal term will be defined as birth between 37 and 41 weeks gestation. Post-term will be defined as birth after 41 weeks gestation.

The following codes are available so we can get banded weeks of gestation.

1518 Duration of pregnancy

Code	Number	
O09.0	<5	Completed weeks
O09.1	5-13	Completed weeks

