O09.2	14-19	Completed weeks
O09.3	20-25	Completed weeks
O09.4	26-33	Completed weeks
O09.5	34-36	Completed weeks
O09.9	Unspecified duration of pregnancy	

The yellow highlights are periods outside of the inclusion criteria.

Codes O09 should also have the following codes assigned for additional diagnoses:

Abortion	O00-007	Pregnancy with abortive outcome
Threatened abortion	O20.0	
Fetal death in utero	O36.4	
Premature rupture of membranes	O42	Before 37 completed weeks of gestation
Threatened premature labour	O47.0	False labour Before 37 completed weeks of gestation
Early onset of labour	O60	Early Preterm labour

Example

Patient admitted at 28 weeks gestation with a diagnosis of fetal death in utero (FDIU)

Medical and surgical induction of labour

O36.4	Maternal care for intrauterine death
O60.1	Preterm labour with preterm delivery
O09.4	Duration of pregnancy 26-33 weeks
Z37.1	Single stillbirth

1527- O48 will indicate prolonged pregnancy post dates and post term.

Some women deliver outside the hospital setting and this is estimated by the MoH at around 2%; however, information about these births is available via the National Maternity

Collection. All births, regardless of delivery setting, are assigned a unique National Health Index number. This allows capture of all post-birth hospital and/or notification events for all infants.

Inclusion criteria

Women

NZ women who are pregnant during the study period

Infants

Infants of the women who were pregnant during the study period

Study Two: Prospective intensive monitoring study of safety in pregnant women administered Tdap vaccination

This is a prospective observational study. It will describe any adverse events in pregnant mothers who received Tdap occurring within one month following immunisation. The data for this part of the study will be collected using the same methodology as that currently being used in Canterbury (i.e., Study Three currently in progress) and will therefore be directly comparable and also joint analysis will be possible for the maternal outcomes.

NOTE: We will not have any cases of spontaneous abortion in Studies Two and Three as the lower gestation eligible for vaccination and therefore inclusion in the study is 28 weeks.

Study population

All women vaccinated during pregnancy at any General Practice in NZ with Tdap vaccine will form the Study Two population.

Study participants

Study Two will include women 28–38 weeks pregnant.

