Women presenting to participating general practices for pertussis vaccine. Practice nurses will be asked to inform all eligible women presenting about the study and with their consent provide their contact details to the research team. Recruitment will continue until the required numbers are achieved at which time practices will be asked to cease recruiting or modify their eligibility criteria.

Practices will be asked to document the following information for women who decline to participate. To identify possible biases between practice and pregnant women who chose to participate versus decliners coded reasons for decline (i.e., too busy, dislike being involved in research), age band, ethnicity and parity will be collected by the recruiting practice nurses. Information will also be collected on the practices that have a higher decline rate. This will include the geographical location, overall socioeconomic band of the practice population and ethnicity mix.

Practice nurses will invite women to be contacted by the study team. Contact details will be obtained from their General Practice only for women who have verbally consented to be contacted. Potential study participants will be identified by fax receipt of a consent to follow up from the General Practice to the investigators. Practices will be provided with a gift voucher for each participant to acknowledge their time.

It is possible that a small percentage of women may have received Tdap from sources other than their GP (e.g., healthcare workers or women who are seen at hospital with wounds that require a tetanus booster). However it is anticipated this will only be a very small proportion as most Emergency Departments and Accident and Emergency Centres in NZ only stock

ADT, not Tdap. Furthermore the records of claims through Ministry will accurately reflect the total number of women in NZ receiving Tdap during pregnancy.

Inclusion criteria for Study Two

Women

Pregnant women who have received the Tdap vaccine during pregnancy between 28 and 38 weeks of gestation.

Compliant with routine antenatal care, including at least one ultrasound early in pregnancy.

Have associated information on the specific vaccines given, including batch number.

Exclusion criteria for Study Two

If a woman has already had her baby prior to being contacted by the study team she will not be enrolled in the study.

Endpoints for Study Two

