Rates and patterns of adverse events in women who were administered Tdap during pregnancy

Multiple pregnancies

While the number of visits during pregnancy could have an impact on the pregnancy outcome within the study population in Study Two and Three (but not in Study One). The frequency of prenatal care is a potential confounder as it may be associated both with women receiving Tdap or not, and with birth outcomes. There is no way to capture the number of prenatal visits women have from nationally available data. However, the National Maternity Collection does “contain data on primary maternity services provided under Section 88 of the NZ Public Health and Disability Act 2000. This information is sourced from lead maternity carer claims for payment.” This information might be useable as a proxy to indicate frequency of prenatal care.

Study Three: Intensive monitoring study of pregnant women administered Tdap during pregnancy and their infants

Study Three involves extending and supporting the intensive monitoring study currently being conducted in the Canterbury DHB by [name] (Principal Investigator). Briefly this study runs as per Study Two except the women and their infants are followed up intensively for a period of one year after the birth of the infant. The data collected for the period of one month post vaccination in Study Three will be able to be pooled for the overlapping subset of participants also in Study Two.

Study Three includes women receiving the vaccine under the DHB programme at 30–36 weeks in the Canterbury region.

Figure 1. Study population and outcomes

[figure not shown]
[figure not shown]

Figure 2. Monitoring of pregnant women receiving pertussis during pregnancy

Canterbury DHB continues intensive follow up for birth outcomes and infant outcomes for one year for a sample of 300 women and their infants. Infant follow up at three to seven months and 12 months of age in this DHB as per Canterbury protocol (Study Three) (Appendix 8).

Study procedures

Study One (utilising whole population data-linking)

Data sets for hospitalisations, pertussis notifications, infant vaccination and maternal Tdap vaccination will be obtained for the period 1 January 2009 to year ending 2013 from the following national databases:

- National Minimum Dataset for hospitalisation data
- The National Immunisation Register for infant immunisation data
- Notification data from the ESR
- Pregnancy Immunisation records from the HealthPAC claims database

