- Estimated minimum and maximum number of women for follow up of pertussis vaccine 1,527–20,358

Sample size and power

As this is an observational study we plan to describe the confidence intervals for the proportions of AEs. With a sample of 300 vaccinated participants, if event occurs in 10% of the group the 95% CI would be 7–14%; if 5%, 2.8–8.1%; if 1%, 0.2–2.9%. Additional power will be achieved by combining the data from the Canterbury study (Study Three), which aims to include 300 women vaccinated with Tdap.

Statistical Analyses

The pregnancy safety data will be descriptive in nature, including percentages and 95% confidence intervals. The rates of AEs and SAEs following pertussis vaccine will be discussed in context with the rates previously described for pertussis. The expected background rates of MAEs and SAEs for Tdap given during pregnancy are unknown, but as a guide the rates of MAEs for pregnant women receiving influenza vaccine previously reported ranged from 1.1 to 3.8% while the rate of SAEs ranged from 0.4 to 1.5%.

Women who have complicated pregnancies will be excluded from the final analyses and described separately.

The temporal relationship between onset of events and vaccination will be presented including distribution where appropriate.

Serious adverse events will be reported as detailed clinical cases. Other events will be groups according to Brighton Collaboration Definitions.

Study Three (N=~300)

From the protocol for Canterbury DHB (Appendix 8): Principal Investigator, [name].

As this study is an observational study, the pregnancy outcomes and safety data will be descriptive in nature. The rates of AEs and SAEs will be compared to published background rates for the general population. The expected rates of MAEs and SAEs for Tdap given during pregnancy is unknown, but as a guide the rates of MAEs for pregnant women receiving influenza vaccine in this paper ranged from 1.1 to 3.8% while the rate of SAEs ranged from 0.4 to 1.5%. Where the known background incidence of 0.01 for a particular adverse event, a sample size of 300 achieves 80% power to detect an additional incidence rate of 0.0175 when the significance level is 0.05.

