Appendix 7: Study Two Phone Survey 2 (4-weeks post vaccine)

PIPS Patient Participant Phone Survey (4 weeks post vaccine)

Researcher: _____ **Date:** _____

The following questions ask about your memory of events for the period up to 4 weeks following when you received the Tdap vaccine (whooping cough vaccine).

	Yes	No	Date started	Date resolved/ recovered	Resolving/ recovering	Not resolved/ recovered	Resolved/ recovered with lasting effects
1. Have you experienced any adverse events/symptoms within the one month post vaccination?							
2. Since receiving the vaccine, have you had any infections such as a: urine, ear, nose, throat, lung infection, gastroenteritis, skin infections							
3. Since receiving the vaccine, have you experienced any of the following:							
Muscle aches and pains							
New onset high blood pressure							
Severe nausea or vomiting							

Pertussis in Pregnancy Safety (PIPS) Study Protocol
 Confidential
 Not for Public Circulation or Reproduction

Premature labour							
Premature rupture of membranes							
Severe abdominal pain							
Vaginal bleeding							
Depression or psychological disorders							
Unexplained itching of the skin							
Spontaneous abortion or threatened abortion							
4. Since receiving the vaccine, have you needed to see a doctor for any of the events described above or for any other reason?		If no, go to end.	If yes, please indicate where you saw the doctor:  Emergency Room/After Hours  Hospital  GP Practice				
4b. What was the diagnosis?							
4c. If there was no diagnosis, what were the signs and symptoms?							

4d. Can we contact your family doctor for further details?
(If yes, please provide Dr name and hospital/practice details)

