Funding for Tdap is being offered postpartum as well as during pregnancy, so women may choose to wait until their babies are born to take up the offer. Funding for the vaccine has approved for an initial period of 6 months with a view to extending for another 6 months if the pertussis outbreak continues. Previous outbreaks in New Zealand have lasted in the order of 18 months so it is likely that funding will continue beyond 6 months. We would therefore aim to enroll 300 women who have received Tdap vaccine.

Study groups

Group 1) received Tdap vaccine while pregnant (30 to 36 weeks gestation).

Group 2) received trivalent inactivated influenza vaccine while pregnant

Group 3) received both Tdap and trivalent inactivated influenza vaccine, separately or coadministered during pregnancy

Inclusion criteria

Women

- Pregnant women 18-40 years of age who have received either the Tdap vaccine between 30-36 weeks gestation, or received the influenza vaccine at any stage during pregnancy or both
- Compliant with routine antenatal care, including at least 1 ultrasound early in pregnancy
- Information regarding which brand vaccine of was given (if the brand is not available, batch number and expiry is sufficient as this will help to ascertain which brand was given)

Infants:

- Infants of the women who were vaccinated with the Tdap vaccine, seasonal influenza vaccine or both during pregnancy

Exclusion criteria

- Pregnant women who have received the Tdap vaccine prior to 30 weeks gestation or after 36 weeks gestation
- If a woman has already had her baby prior to being contacted by the the study team, she will not be enrolled in the study

Statistical Analysis

As this study is an observational study, the pregnancy outcomes and safety data will be descriptive in nature. The rates of AEs and SAEs will be compared to published background rates for the general population (summarised in Tavares et al¹⁰). The expected rates of MAEs and SAEs for Tdap given during pregnancy is unknown, but as a guide the rates of MAEs for pregnant women receiving influenza vaccine in this paper ranged from 1.1 to 3.8% while the rate of SAEs ranged from 0.4 to 1.5%. Where the known background incidence of 0.01 for a particular adverse event, a sample size of 300 achieves 80% power to detect an additional incidence rate of 0.0175 when the significance level is 0.05.

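### Study Two's preterm-type event percentages would include women vaccinated at 37–38 weeks, and for these events Study Two is not directly comparable with Study Three

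*Protocol*

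**What the plan says.** All references are to the Protocol.

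- **Study Two window** (Inclusion criteria for Study Two): "Pregnant women who have received the Tdap vaccine during pregnancy between 28 and 38 weeks of gestation". Appendix 1 repeats it.
- **Events asked about** (Appendix 7, four-week phone survey): the list includes "Premature labour" and premature rupture of membranes. Neither item carries a gestation limit.
- **Cut-off** (Study One, Outcomes): "Preterm will be defined as birth before 37 weeks gestation". The Study One code list attaches a limit of 37 completed weeks to premature rupture of membranes (O42) and to threatened premature labour (O47.0). The O60 row for preterm labour gives no week number.
- **Analysis** (Study Two, Sample size and power): "we plan to describe the confidence intervals for the proportions of AEs". Precision is illustrated on 300 vaccinated participants. The same paragraph expects extra power from combining the data with Study Three's 300 women and states no gestational restriction.
- **Comparability** (opening of the Study Two section): because data collection follows the Canterbury method, the data will be "directly comparable and also joint analysis will be possible for the maternal outcomes".
- **Pooling** (Study Three section): "The data collected for the period of one month post vaccination in Study Three will be able to be pooled". The sentence goes on to confine this to an overlapping subset of participants who are also in Study Two.
- **Study Three window** (same section): "Study Three includes women receiving the vaccine under the DHB programme at 30–36 weeks in the Canterbury region". The exclusion criteria in Appendix 8 remove "Pregnant women who have received the Tdap vaccine prior to 30 weeks gestation or after 36 weeks gestation".

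**The concern.** A percentage describes risk only if the women in the denominator could have had the event. At the lower end of the window the Protocol reasons this way itself: it notes that Studies Two and Three will see no spontaneous abortions because eligibility starts at 28 weeks. It does not apply the same reasoning at the upper end, where women vaccinated at 37 or 38 weeks are already past the preterm cut-off.

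Two things are at stake. First, the Study Two percentages for preterm-type events would be too low as a description of women at risk, and the error runs in the direction of the Protocol's clinical hypothesis of similar event rates. Secondly, Studies Two and Three would differ on these events, and a combined figure would mix two different amounts of time at risk, even if the underlying risk were identical.

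**Working it through.** **1. The Protocol's own figures.** Exact (Clopper-Pearson) 95% intervals for 30, 15 and 3 events in 300 are 6.8–14.0%, 2.8–8.1% and 0.2–2.9%. These match the stated 7–14%, 2.8–8.1% and 0.2–2.9%. No stated figure is wrong.

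**2. Dilution within Study Two.** Let f be the share vaccinated at 37+0 weeks or later. Then reported rate = rate among women at risk × (1 − f). The Protocol does not give f. For a true 5.0%:

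| Assumed f | Women at risk of 300 | Reported rate |
|---|---|---|
| 5% | 285 | 4.75% |
| 10% (even spread, window ends at 38+0) | 270 | 4.5% |
| 2/11 = 18% (even spread over completed weeks 28–38) | about 245 | 5.0 × 9/11 = 4.1% |
| 30% | 210 | 3.5% |

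**3. Time at risk compared with Study Three.** Inputs are the two windows, four weeks of follow-up and the 37-week cut-off. A woman vaccinated at week w has min(4, 37 − w) weeks at risk, and none from 37 onwards. With vaccination spread evenly over completed weeks:

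- Study Two (28.0–39.0): (5 × 4 + 8)/11 = 28/11 = 2.55 weeks.
- Study Three (30.0–37.0): (3 × 4 + 8)/7 = 20/7 = 2.86 weeks.
- Ratio: 2.55/2.86 = 0.89.

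If both windows end at the start of their last week (28.0–38.0 and 30.0–36.0), the means are 2.80 and 3.25 weeks, ratio 0.86. If weekly risk is assumed to double every four, three or two weeks of gestation, the ratio falls to between 0.78 and 0.70. Over all these scenarios, equal underlying risk would show 11–30% fewer preterm-type events in Study Two.

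**4. Which women cause the gap.** Removing only those at 37–38 weeks leaves Study Two with 28/9 = 3.11 weeks. The ratio becomes 3.11/2.86 = 1.09, on the other side of 1. Over all the scenarios in step 3 it lies between 0.78 and 1.09. The 28–29 week women, whom Study Three does not enrol, therefore matter too. Shortened time at risk after 33 weeks occurs in both studies.

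**5. Precision after restriction.** With f = 2/11 and 12 events, 12/300 = 4.0% (2.1–6.9%) becomes 12/245 = 4.9% (2.6–8.4%). The interval widens from 4.8 to 5.8 percentage points.

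**The case against.** The case on the other side is substantial, and parts of it stand.

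- **The survey sets no limit.** The 37-week notes belong to Study One's definitions and code list. A reader might infer that women at 37–38 weeks cannot have either event. That is firm for premature labour on its ordinary meaning, but it holds for membrane rupture only if the item is read as before 37 weeks. The Study One list supports that reading by attaching the limit to the same term; the survey form does not state it.
- **The denominator is only illustrated.** An analysis plan not shown here might define event-specific risk sets. Even so, the Protocol frames its proportions on the whole vaccinated group and names no exception.
- **Comparability rests on shared methods.** A reader might infer that the two studies cannot be compared or pooled at all. The documents do not support that: local reactions, fever and other events without a gestation bound are unaffected. The pooling sentence also carries a restriction, but it is ambiguous. It can mean shared gestations or women enrolled in both studies, and the sample-size paragraph combines the data without repeating it.
- **The analysis is descriptive.** There is no unvaccinated comparator in Study Two and no planned test against Study Three, and serious events are to be reported as clinical cases. A reader might infer that the plan makes the vaccine look safer than it is; the documents support only that a few percentages would be understated. A four-week percentage over all women in the funded 28–38 week programme is a legitimate description of that programme. It is just not the risk among women who can have the event.
- **The shift is small beside the sampling error.** A move from 5.0% to 4.1% is about three women and lies inside the planned 2.8–8.1%. That is so, but the shift is systematic and pooling does not remove it.

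**Conclusion.** The point holds for premature labour, and for premature rupture of membranes if that is read as before 37 weeks. The understatement equals the share of women vaccinated at 37–38 weeks. The Protocol does not give this share, so its size is an assumption: a true 5.0% reads 4.75–3.5% over 5–30%, and 4.1% under even spread. For these events the unqualified statement of direct comparability with Study Three does not hold. The 11–30% gap under equal risk rests on evenly spread vaccination and on constant or rising weekly risk.

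Two further inferences would go too far. The 28–38 week inclusion window is not itself an error; it follows the national funded programme, and the remedy lies in the analysis. Nor are the 37–38 week women the whole explanation of the mismatch, since dropping them alone leaves a ratio of 0.78–1.09.

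Two other rules could also distort preterm-type rates and are not cured by this change: women who delivered before first contact are not enrolled, and complicated pregnancies are removed from the final analyses.

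**What to change.** In the Study Two statistical text:

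1. Report premature labour and premature (preterm) rupture of membranes among women vaccinated before 37+0 weeks, and state that the membrane item is read as before 37 weeks. Gestation at vaccination follows from the due date and vaccination date on the Appendix 3 referral form.
2. Compare or pool these events with Study Three only for women vaccinated at 30–36 weeks in both studies. The Canterbury practice form also records both dates. This removes the difference in windows, though not any difference in how vaccination is spread within 30–36 weeks.
3. Qualify the comparability statement at the start of the Study Two section accordingly, and say what the overlapping subset in the Study Three section means.
4. Keep the full 28–38 week set for local and systemic reactions.

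A rate per woman-week ended at delivery is not proposed: the Study Two forms have no delivery date, and preterm delivery is not a survey item.

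The cost is wording, plus a smaller denominator and a somewhat wider interval for these few events (about one percentage point in the example above). No new data are needed.
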